Study Duration:	2.5 years: 1 year for planned accrual + 1.5 year for postpartum follow-up
Study Medication:	Fixed-dose combination tablet of 400 mg of Sofosbuvir and 100 mg of Velpatasvir (SOF/VEL)
Study Regimen:	Participants will take SOF/VEL one tablet once daily starting within their first 12 months postpartum for 12 weeks total.

Primary Objective:

- Evaluate the feasibility/acceptability of a combined, peripartum HCV and opioid maintenance treatment clinical protocol on adherence to HCV treatment regimens

Primary Endpoint:

- Treatment feasibility will be established through the successful recruitment and enrollment of participants, administration of sofosbuvir/velpatasvir in the postpartum period and ability to determine SVR at 3 months following treatment completion.
- Acceptability of sofosbuvir/velpatasvir will be evaluated by self-report of treatment side effects and barriers and facilitators to treatment adherence.
- Adherence to sofosbuvir/velpatasvir will be evaluated with medication diaries, an assessment of missed doses, pill counts and attendance at opioid maintenance treatment visits.

Secondary Objectives:

- To investigate SOF/VEL drug levels in breast milk.
- Evaluate the rate of IVDU recidivism, HCV reinfection and health related QOL in women with OUD during the first postpartum year.

Secondary Endpoints:

- Breast milk concentrations of SOF, the SOF metabolite GS-331007 and VEL
- Rates of IVDU recidivism
- HCV reinfection
- Patient centered outcomes such as health related QOL will be assessed at 6, 9 and 12 months following treatment completion

Table 1: Study Visit Schedule

	Study Visit	Time Period*
V1	Screening A	6 weeks 0 days to 12 months PPM
V2	Screening B	6 weeks 0 days to 12 months PPM

V3	Enrollment	6 weeks 0 days to 12 months PPM
V4**	Treatment initiation	1 day PPM – 12 months PPM
VPK1-5***	Breastmilk PK visits	2-10 days PPM
V5	2 week treatment follow-up	14 days after treatment initiation
V6	4 week treatment follow up	28 days after treatment initiation
V7	6 week treatment follow-up	42 days after treatment initiation
V8	8 week treatment follow-up	56 days after treatment initiation
V9	10 week treatment follow-up	70 days after treatment initiation
V10	End of Treatment Visit 12 weeks treatment follow-up	84 days after treatment initiation
V11	SVR Visit 3 months post-treatment follow-up	6 months after treatment initiation
V12	9 months post-treatment follow-up	12 months after treatment initiation

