V13	End of Study 15 months post-treatment follow up	18 months after treatment initiation

*These are target windows. If the participant cannot be seen within these windows then it will not be considered a protocol deviation

**Start SOF/VEL and continue for 12 weeks

***For a subset of participants, n=5

KEY ROLES

Protocol Identification

Protocol Title: Management of HCV infection in pregnant and postpartum women with OUD: the potential of an integrated medical home model

Short Title: Chronic Hepatitis C treatment with Sofosbuvir/Velpatasvir for postpartum women with OUD

Date: May 10, 2017

Funders, Sponsor and Monitor Identification

Funding Agency: Gilead Sciences Investigator Initiated Studies Program

Site Monitoring: [name] MSc

Pharmaceutical Collaborator: Gilead Sciences

INTRODUCTION

Background

Intravenous drug use (IVDU) is the leading cause of new Hepatitis C virus (HCV) infections and is widespread among pregnant women with OUD. HCV screening during pregnancy is recommended for women with risk factors for HCV exposure and provides a unique opportunity to identify the virus among high-risk women of reproductive age. HCV positivity in pregnant women with OUD ranges from 40-75% and over 28% are newly diagnosed with HCV during pregnancy. Pregnancy is a unique opportunity to engage HCV-infected women in efforts to improve their health and facilitate HCV treatment. However, less than 2% of HCV-infected pregnant patients initiate HCV treatment within one year following delivery.

Rationale

Incorporating HCV treatment into opioid maintenance treatment program clinical protocols is an innovative health care delivery model that has been associated with improved HCV treatment uptake in non-pregnant, drug-using populations. This “medical home” approach would combine HCV and opioid maintenance treatment into one treatment regimen and incorporate the expertise of obstetricians, hepatologists, substance abuse treatment providers and pediatricians into one comprehensive clinical care model. We hypothesize that co-locating prenatal care, HCV treatment and substance abuse treatment services in the same clinical environment will significantly improve HCV treatment uptake and compliance as well as facilitate ongoing recovery from opioid addiction.

SOF/VEL Fixed Dose Combination

Description

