 - b. Hemoglobin less than 10 g/dL immediately prior to treatment initiation
 - c. Platelet count less than 90,000 per mm³ immediately prior to treatment initiation
 - d. International normalized ratio (INR) > 1.5
 - e. GFR < 40

- 6) Has any other condition that, in the opinion of the IoR/designee, would preclude informed consent, make study participation unsafe, complicate interpretation of study outcome data, or otherwise interfere with achieving study objectives.

STUDY MEDICATION

Regimen

Each participant will take a 12 week course of SOF/VEL one tablet by mouth, once daily.

Administration

Study medication will be dispensed in the immediate postpartum period in the quantities sufficient to have one dose per day until the next scheduled visit with 2 extra doses. Tablets will be packaged by the Investigational Pharmacist/Pharmacist of Record (PoR) in the pharmacy at Magee-Womens Hospital. Participants will be given a medication administration log to assist them with keeping track of when they took their doses. The medication administration log will include instructions on timing of the dose, what to do if a dose is missed and how to store the medication. If a dose is missed, they should take the dose as soon as it is remembered, but only one dose per day. Participants will be instructed to take their medication in the morning each day at the same time, preferably early in the morning. SOF/VEL can be taken with or without food. Additionally, participants will be given adherence tips, such as setting an alarm on their phone, linking medication taking to another daily activity, etc. Participants will be instructed to bring any unused medication to their next visit. Participants will be instructed to call the study staff immediately if they run out of medication or if they lose their study medication. In this case, all possible efforts will be made to get the participant study medication as soon as possible.

Supply and Accountability

Supply

Gilead Sciences will manufacture the study medication under Good Manufacturing Practices (GMP) and will package, label and ship all of the study medication directly to the PoR at Magee-Womens Hospital.

Storage and Dispensing

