The following procedures will occur at the End of Treatment visit. This visit will be scheduled within 7 days of completion of the 12 week course of study medication. The purpose of this visit will be to collect any remaining study medication and to collect and follow up on any adverse events.

Table 10: End of Treatment Visit

End of Treatment Visit (12 week postpartum follow-up, V10)	
Component	Procedures
Administrative and Regulatory	
 • Review/update locator information • Visit Questionnaire • Record/update AEs • Schedule next visit
Behavioral	
 • Collect remaining study medication and medication administration log • Conduct qualitative interview
Clinical	
 • Review/update medical history • Review/update concomitant medications • Consultation with hepatologist (only if HCV virus not cleared at 8w) • Provide test results if available
Laboratory	
 • HCV RNA • CMP, CBC, GGT

SVR Assessment (3 month post-treatment visit, V11)

The following procedures will occur at the 3 month post-treatment visit

Table 11: SVR Assessment (V11)

SVR Assessment (3 month post-treatment visit, V11)	
Component	Procedures
Administrative and Regulatory	
 • Review/update locator information • Visit Questionnaire • Record/update AEs • Schedule next visit • Conduct qualitative interview
Clinical	
 • Review/update medical history • Provide test results if available • Consultation with hepatologist (by phone)
Laboratory	
 • HCV RNA • CMP, CBC, GGT

9 month post-treatment visit (V12)

The following procedures will occur at the 9 month post-treatment visit (V13)

Table 13: 9 month post-treatment visit (V12)

V13: 9 month post-treatment visit	
Component	Procedures
Administrative and Regulatory	
• Review/update locator information• Review infant demographics/sign release(s) for medical records for infant (if necessary)• Schedule next visit
Clinical	
• Review/update medical history• Provide available test results
Laboratory	
• HCV RNA• CMP, CBC, GGT

End of Study Visit (15 month post-treatment visit, V13)

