APPENDIX

APPENDIX I: SCHEDULE OF STUDY VISITS AND EVALUATIONS

	Screening A (V1)	Screening B (V2)	Enrollment (V3)	Treatment Initiation (V4)	Breastmilk PK Visits*	Treatment Follow Up (V5-9)	End of Treatment (V10)	Post treatment (V11)	12 month follow up (V12)	End of Study (V13)
ADMINISTRATIVE AND REGULATORY										
Informed consent(s)	X		X		X					
Assess informed consent comprehension			X							
Sign medical record releases	X			X					X	X
Assignment of PTID			X							
Collect/review locator information	X	X	X	X	X	X	X	X	X	
Visit questionnaire		X				X	X	X		X
Eligibility assessment	X	X								
Eligibility confirmation		X	X	X						
Reimbursement					X					
Record/ update AEs					X	X	X	X	X	X
Schedule next visit	X	X	X	X	X	X	X	X	X	
BEHAVIORAL										
Protocol adherence counseling		X	X	X	X	X	X	X	X	
Contraception counseling					X					
Medication use/adherence counseling					X	X	X	X		***
Qualitative interview							X			X
CLINICAL										
Review medical history and medical records, document findings	X	X	X	X		X	X	X	X	X
Concomitant medications	X	X	X	X		X	X			
Consult with hepatologist		X	X				***	X		
Physical examination (full or modified)		X	X							
Provide available test results			X	X		X	X	X	X	X
Administer timed medication dose					X					
LABORATORY										
Collect breastmilk					X					
Collect Blood		X		X	X	X	X	X	X	
HCV antibody	X**									
HCV RNA viral load	X**					X (V6 or 7)	X	X	X	
HCV Genotype		X**								
HCV Resistance testing							***	***		
HepBsAg	X**									
HepBcAb, HepBsAb		X								
HepA total Ab		X								
HIV	X*									
CBC				X*		X (V6 or 7)	X	X	X	
CMP		X		X*		X (V6 or 7)	X	X	X	
GGT				X		X (V6 or 7)	X	X	X	
PK sampling breastmilk and blood					X					
STUDY MEDICATION										
Provision of Study Medication				X	X	X				
Collect Remaining Study Medication							X			

*For a subset of participants, n=5 **If not collected as part of standard prenatal/postpartum care; can be collected at V2 if within 3 months of treatment initiation ***If clinically indicated

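### The quality-of-life endpoint is set at 6, 9 and 12 months after treatment, but visits fall at 3, 9 and 15 months and the 9-month visit lists no questionnaire

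*Combined protocol and SAP*

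**What the plan says.** The endpoint appears in identical words in the Summary (Secondary Endpoints), in Study Design (Summary of Major Endpoints) and in Statistical Considerations (Secondary Endpoints): "Patient centered outcomes such as health related QOL will be assessed at 6, 9 and 12 months following treatment completion".

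Table 1 gives three visits after end of treatment: V11, "SVR Visit 3 months post-treatment follow-up"; V12, "9 months post-treatment follow-up"; and V13, "End of Study 15 months post-treatment follow up". It also dates them at 6, 12 and 18 months after initiation.

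The visit-level sources say the following about questionnaires:

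- **V11:** Table 11 lists one, and Appendix I marks one.
- **V12:** Table 13 lists none. Its administrative items are locator information, scheduling, and "Review infant demographics/sign release(s) for medical records for infant (if necessary". The row "Visit questionnaire" in Appendix I is blank at V12. The text above Table 13 uses an old visit number ("The following procedures will occur at the 9 month post-treatment visit (V13"), but the month label leaves no doubt which visit is meant.
- **V13:** Appendix I marks a questionnaire; Table 14 lists none.

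The Data Analysis section says that validated instruments will measure QOL. It names none and ties none to a visit.

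**The concern.** An endpoint with fixed assessment times needs a scheduled collection at each of them. Here two of the three times have no visit, and the third has a visit with no listed means of collecting a QOL score.

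Staff who follow the visit tables would have no instruction to collect QOL at any stated time. The analyst would then have to attach scores from other times to the endpoint after the fact, or report it as not assessed. Laboratory results can often be found later in the medical record, but a participant's self-reported QOL cannot.

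**Working it through.** **Inputs.** Stated QOL times: 6, 9 and 12 months after completion (the three endpoint lists). Course length: 12 weeks, from the Regimen section ("Each participant will take a 12 week course of SOF/VEL one tablet by mouth, once daily"). Visits: 6, 12 and 18 months after initiation (Table 1). Questionnaires: Tables 11, 13 and 14 and Appendix I.

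**Step 1: reproduce the plan's visit labels.** 12 weeks = 84 days; 84 / 30.44 = 2.76 months. Months after completion = months after initiation − 2.76:

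- V11: 6 − 2.76 = 3.24
- V12: 12 − 2.76 = 9.24
- V13: 18 − 2.76 = 15.24

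These agree with the labels of 3, 9 and 15 months, so Table 1 is consistent with itself. The mismatch lies between Table 1 and the endpoint.

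**Step 2: match each stated time to a visit and to a questionnaire (Appendix I).**

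| Stated time (months after completion) | Nearest visit | Gap (months) | Nearest visit with a questionnaire | Gap (months) |
|---|---|---|---|---|
| 6 | V11 | 6 − 3.24 = 2.76 | V11 | 2.76 |
| 9 | V12 (no questionnaire) | 9.24 − 9 = 0.24 | V11 | 9 − 3.24 = 5.76 |
| 12 | V12 (no questionnaire) | 12 − 9.24 = 2.76 | V13 | 15.24 − 12 = 3.24 |

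Only the 9-month time coincides with a visit, and that visit has no questionnaire. If QOL is collected through the visit questionnaire, 0 of 3 stated times are scheduled. If Table 14 rather than Appendix I is right about V13, the nearest questionnaire to 12 months is V11, a gap of 12 − 3.24 = 8.76 months.

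**Step 3: try the other readings.**

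- *Months counted from initiation.* 6 months is V11, with a questionnaire. 9 months has no visit. 12 months is V12, without a questionnaire. That gives 1 of 3, and it contradicts the endpoint's own reference to completion.
- *Appendix I's label for V12 as a 12-month follow-up.* This fits a count from initiation. The questionnaire cell is blank whichever way it is read.
- *Target windows.* Table 1 says a visit outside its window is not a deviation, and it gives no width for V11 to V13. V11 would have to move by about 2.8 months to serve as a 6-month assessment, yet it is also the 3-month SVR visit.
- *Interim visits.* These are allowed at any time, but procedures are repeated there only on clinical grounds. They schedule nothing.
- *Qualitative interview.* The documents place it variously at V10, V11 and End of Study, never at 6, 9 or 12 months after completion. Its topics are infection, risk behaviour and treatment, not a QOL score.

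**The case against.** The strongest reply is that nothing in the documents says QOL is collected through the visit questionnaire. The Data Analysis section leaves the instrument free of any visit. The section on source documents provides for tracking the dates of surveys and the method of contact used to complete follow-up assessments. Collection between visits is therefore possible.

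The tables are also imperfect evidence. Tables 7 and 8 list a questionnaire at V4 and at the PK visits, where Appendix I has no mark. Appendix I marks adverse event recording at V12 and V13, where Tables 13 and 14 omit it. A blank cell does not prove that nothing was intended.

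Much of this stands. A reader might infer that none of the three time points can be filled, or that 0 of 90 assessments (30 women × 3 times) will exist. The documents do not support that: they show that no QOL collection is scheduled at those times, not that it is impossible. A reader might also infer that scores taken by phone or email would be unusable. Nothing in the documents says so, and the End of Study visit already permits those modes.

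The objection does not remove the mismatch. Two sources agree that V12 has no questionnaire, no source has a visit at 6 or 12 months, and a survey that could be sent between visits is not one that the plan schedules.

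**Conclusion.** The endpoint and the schedule contradict each other. There is no visit at 6 or 12 months after completion, and no QOL instrument is assigned to the 9-month visit. Those facts need no assumption.

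The count of 0 of 3 stated times scheduled rests on the assumption that the visit questionnaire carries the QOL instrument. Counting from initiation, it is 1 of 3. By the plan's own visit labels, the nearest questionnaires are 3, 6 and 3 months from the stated times, with the last figure depending on Appendix I being right about V13.

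This should be fixed, but it does not threaten the trial. QOL is a secondary endpoint with a descriptive analysis in a single-arm pilot of 30 women. No sample size or test depends on it, and the primary endpoints, SVR, safety and pharmacokinetic assessments are unaffected.

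**What to change.** 1. In the three endpoint lists, restate the QOL times as the visits that exist: 3, 9 and 15 months after treatment completion (V11, V12, V13).
2. Name the validated QOL instrument and assign it to those visits. Add it to V12 in both Table 13 and Appendix I.
3. Reconcile V13, where Appendix I has a questionnaire and Table 14 does not. Correct the leftover visit numbers at the same time.
4. If 6 and 12 months are to be kept, schedule remote administration at those times, and still add the instrument to V12 for the 9-month time.

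Steps 1 to 3 cost protocol wording and one added questionnaire for participants at a visit they already attend, with no new visit. Step 4 would instead add two remote contacts per woman.

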 - b. Hemoglobin less than 10 g/dL immediately prior to treatment initiation
 - c. Platelet count less than 90,000 per mm³ immediately prior to treatment initiation
 - d. International normalized ratio (INR) > 1.5
 - e. GFR < 40

- 6) Has any other condition that, in the opinion of the IoR/designee, would preclude informed consent, make study participation unsafe, complicate interpretation of study outcome data, or otherwise interfere with achieving study objectives.

STUDY MEDICATION

Regimen

Each participant will take a 12 week course of SOF/VEL one tablet by mouth, once daily.

Administration

Study medication will be dispensed in the immediate postpartum period in the quantities sufficient to have one dose per day until the next scheduled visit with 2 extra doses. Tablets will be packaged by the Investigational Pharmacist/Pharmacist of Record (PoR) in the pharmacy at Magee-Womens Hospital. Participants will be given a medication administration log to assist them with keeping track of when they took their doses. The medication administration log will include instructions on timing of the dose, what to do if a dose is missed and how to store the medication. If a dose is missed, they should take the dose as soon as it is remembered, but only one dose per day. Participants will be instructed to take their medication in the morning each day at the same time, preferably early in the morning. SOF/VEL can be taken with or without food. Additionally, participants will be given adherence tips, such as setting an alarm on their phone, linking medication taking to another daily activity, etc. Participants will be instructed to bring any unused medication to their next visit. Participants will be instructed to call the study staff immediately if they run out of medication or if they lose their study medication. In this case, all possible efforts will be made to get the participant study medication as soon as possible.

Supply and Accountability

Supply

Gilead Sciences will manufacture the study medication under Good Manufacturing Practices (GMP) and will package, label and ship all of the study medication directly to the PoR at Magee-Womens Hospital.

Storage and Dispensing

SOF/VEL should be stored at room temperature below 30°C within the main pharmacy at Magee-Womens Hospital¹. The PoR will maintain documentation of temperature in the area where the study medication is stored. Study medications will be dispensed from the pharmacy in a small bottle until the next study visit with two additional doses in the case of a lost dose or missed study visit. Study medications will be dispensed from the pharmacy only upon receipt of a written prescription from an authorized prescriber. The study medication will be dispensed to the study staff, then subsequently provided directly to the study participant in the research clinic.

Accountability

The PoR will maintain complete accountability records of all study SOF/VEL FDC received and dispensed. All unused study medications will be returned to Gilead Sciences after the study is complete.

Retrieval of Study Medication

The participants will be instructed to return any unused medication at each visit. If the participant fails to return unused medication at a scheduled visit, alternate arrangements will be made to obtain the unused medication from the participant (i.e. at an unscheduled visit). Unused medication will be accounted for by the clinician, documented in the participant's research record and then returned to the PoR.

Concomitant Medications

SOF/VEL in postpartum women with OUD, Version 8.0

June 11, 2019

Enrolled study participants may use non-prohibited concomitant medications during study participation. All concomitant medications reported throughout the course of the study will be recorded on case report forms designated for that purpose. All prescription medications and over-the-counter preparations including vitamins will be recorded on forms for concomitant medications. Participants will be prohibited from using nutritional supplements, herbal preparations and medications contraindicated for concomitant use with Sofosbuvir and Velpatasvir as described in the package insert. Each reported medication will be reviewed to ensure the participant is not using prohibited medications as referenced in the Epclusa package insert. At each visit, participants will be asked if they have initiated any new medications or changed any reported medications. If the participant reports using acid suppressing medications, specific dosing instructions will be reviewed regarding correct timing of acid suppressing medication use according to the Epclusa package insert.

STUDY PROCEDURES

An overview of the study visit and evaluations schedule is presented in Appendix 1. Any clinical or laboratory information collected as a part of the participant's routine clinical care occurring on the same day as the study visit does not need to be repeated and can be collected from the participant's medical record.

Pre-screening

With IRB approval, study staff will pre-screen records to identify potential participants by evaluating minimum criteria (i.e. age, gestational age, Hepatitis C status). Clinic staff will be informed of the study and will be asked to provide an IRB-approved material to potential participants or will assess interest. If the participant agrees, research staff can provide additional information by reviewing an IRB-approved screening script, which will include a brief overview of the study and minimum eligibility questions. Women who are interested and qualify based on the screening script may schedule a screening visit if interested. Process information (e.g., number of potential participants contacted, number presumptively eligible) may be recorded and stored at the study site in the absence of written informed consent from potential participants, provided the information is collected in such a manner that it cannot be linked to participant identifiers. Procedures and documentation will comply with the University of Pittsburgh IRB requirements. IRB approved ads and flyers may also be used (i.e. hung throughout the hospital; displayed on electronic boards; emailed to providers or appropriate support or community groups).

Visit 1- Screening A (V1)

Screening Visit A can take place anytime with the screening window. Multiple visits may be conducted to complete all required screening procedures, if necessary. Written informed consent will be obtained before any screening procedures are initiated. All participants will meet with hepatology who will ultimately determine whether to initiate hepatitis C treatment in the immediate postpartum period and participants will be encouraged to discuss participation in the study with hepatology. For participants who subsequently do not meet the eligibility criteria, screening will be discontinued once ineligibility is determined. Any exclusionary laboratory values can be repeated at a later date within the screening window. If the repeated laboratory values meet inclusion criteria then the participant can be enrolled. If there is concern that the participant's health status has changed between the enrollment visit and the screening visit or if there is concern by the study investigators that the participant might not remain eligible, the screening laboratories can be repeated prior to enrollment.

Table 4: Screening Visit A (V1)

Visit 1- Screening Visit A	
Component	Procedures
Administrative and Regulatory	
 • Review and obtain written informed consent for screening • Sign appropriate medical record releases (i.e. to obtain records from the Pregnancy Recovery Center; outside records as necessary) • Collect contact information • Screening Questionnaire • Assess eligibility • Provide reimbursement for screening visit • Schedule next visit
Clinical	
 • Collect medical history & review medical/prenatal records including documentation of chronic Hepatitis C, Opioid Use Disorder and gestational age/dating
Laboratory	
 • Collect blood 
 – HCV antibody* – HCV RNA* – HBsAg* – HIV*

*If not already available in the medical record 6 months prior to Screening A visit or not anticipated to be obtained by their primary health care provider prior to enrollment

Visit 2- Screening B (V2)

The following procedures will occur at the Screening B visit. Screening Visit B can take place anytime with the screening window. All patients who meet basic eligibility criteria [chronic HCV, OUD, HIV negative, appropriate GA] will meet with Hepatology, who will conduct a full medical history and physical exam and ultimately determine if the patient is eligible to participate in the study. Participants will also complete the baseline assessment at this visit.

Table 5: Screening Visit B (V2)

Visit 2- Screening Visit B	
Component	Procedures
Administrative and Regulatory	
 • Review written informed consent for screening • Review/update locator information • Overview of study procedures/treatment regimen if participant chooses to enroll • Schedule next visit (Enrollment visit with hepatology) if appropriate • Complete Baseline Questionnaire
Clinical	
 • Collect medical history & review medical/prenatal records including documentation of chronic Hepatitis C and gestational age/dating • Review of concomitant medications •
Laboratory**	
Collect blood
 
 – HCV genotype* – HepBcAb* – HepBsAb* – HepB DNA (only if surface antigen and core Ab positive)* – HepA total antibody* – PT/INR – CMP*

*If not already available in the medical record 6 months prior to Screening B visit or not anticipated to be obtained by their primary health care provider prior to enrollment

** Please note, if treatment initiation (V4) is occurring within 3 months of Screening B (V2), treatment initiation labs can be drawn at V2

Enrollment (V3)

The following procedures will occur at the Enrollment visit (V3). The Enrollment Visit may occur between 6+0 weeks gestational age and 12 months postpartum. During the enrollment visit the participant will meet with the hepatologist, and sign the informed consent form.

Table 6: Enrollment (V3)

Enrollment Visit- Visit 3 (V3)	
Component	Procedures
Administrative and Regulatory	
• Confirm eligibility• Review/update locator information• Review and obtain written informed consent for treatment• ICF Comprehension Assessment• Assign participant ID (PTID)• Schedule next visit
Clinical	
• Review/update medical history, review medical record, document pre-existing conditions• Instruct participants to contact study staff when in labor/being admitted to MWH labor and delivery if appropriate• Provide Screening test results• Review of concomitant medications• Consultation with hepatologist• Physical exam
Laboratory	
• None

Treatment Initiation (V4)

The treatment initiation visit will occur in the immediate postpartum period (1-14 days postpartum) or within 12 months postpartum if breastfeeding. Please note, if treatment initiation (V4) is occurring within 3 months of Screening B (V2), treatment initiation labs can be drawn at V2. During the treatment initiation visit the participant will be given instructions on using and begin taking the study medication.Table 7: Treatment Initiation (V4)

Treatment Initiation Visit- Visit 4 (V4)	
Component	Procedures
Administrative and Regulatory	
 • Confirm eligibility • Review/update locator information • Sign appropriate infant medical record releases • Completed visit questionnaire • Schedule next visit
Behavioral	
 • Provide counseling 
 • Protocol adherence • Study medication use/adherence
Clinical	
 • Review/update medical history • Review/update concomitant medications • Provide contraceptive counseling • Provide available test results • Obtain urine pregnancy test
Medications	
 • Participants will receive study medication (supply enough for next visit plus 2 extra doses) • Participants will receive instructions for medication use • Participants will receive medication adherence log
Laboratory	
 • CMP* • CBC* • GGT* •

*If not already available in the medical record 3 months prior to Treatment Initiation Visit

Breastmilk Pharmacokinetics Substudy

A subset of women (n=5) will participate in a sub-study to determine the quantity of drugs (SOF and VEL) transferred into breastmilk. Because the drug has not been studied in infants, all expressed milk will be maintained by the study. We ask each of the 5 women to express 5 samples of breastmilk and have paired blood samples collected at their convenience. Samples will be obtained starting at least 6 hours after the first dose and no sooner than 6 hours from a previous sample. All samples will be obtained by day 10 postpartum. The time of prior SOF/VEL dosing will be carefully recorded as well as the time of the breastmilk and blood collection.

Participants will be instructed to take their daily dose at home as usual. This subsample of participants will be given a pill box (Wisepill) that tracks drug timing so that we have accurate time stamp for when the drug was taken. This is important for the PK study to ensure women were adherent with the medication and to track the time of prior doses in relation to milk and blood collection.

Women will be asked to only express milk when they are at Magee-Womens Hospital under the supervision of the study staff. Women will be asked to express until both breasts are soft and the milk expression rate slows. Because women will be pumping infrequently, their milk volume will diminish and by 10 days, will be of limited volume. Individual venipuncture(s) will be used to collect all plasma samples, and participants will be instructed on how to pump to obtain breastmilk samples.

Case report forms will be completed for each set of breastmilk and blood samples obtained. Two 5-mL breastmilk samples will be processed and stored. One 5-mL aliquot of whole intact milk will be transferred to a cryovial and stored. The second 5-mL aliquot will be centrifuged, the lipid layer removed and transferred to a cryovial and the remaining fluid transferred to a separate cryovial. All three cryovials will be stored at -80°Celcius until shipment to the Colorado Antiviral Pharmacology Laboratory for analysis. 5-mL of blood will be

obtained in a K2 EDTA tube and centrifuged, the plasma transferred to a cryovial and stored at -80°Celcius until shipment to the Colorado Antiviral Pharmacology Laboratory.

SOF, the SOF metabolite GS-331007 and VEL will be measured in plasma and breastmilk using validated LC/MS-MS methods at the Colorado Antiviral Pharmacology Laboratory.

Table 8: Breastmilk Pharmacokinetics Visits (PK1-5)

Breastmilk Pharmacokinetics Visits (PK1-5)	
Component	Procedures
Administrative and Regulatory	
 • Review/update locator information • Visit questionnaire • Provide reimbursement for study visit • Record/update AEs • Schedule next visit
Behavioral	
 • Adherence assessment • Provide modified counseling 
 – Protocol adherence – Study medication use/adherence
Clinical	
 • Administer timed dose of study medication • Adherence assessment
Laboratory	
 • Collect blood (all visits) • Collect breastmilk sample (all visits)

Follow up postpartum visits (Visits 5-9)

- 1) 2 week treatment follow-up (V5): 14 days after treatment initiation
- 2) 4 week treatment follow-up (V6): 28 days after treatment initiation
- 3) 6 week treatment follow-up (V7): 42 days after treatment initiation
- 4) 8 week treatment follow-up (V8): 56 days after treatment initiation 10 week treatment follow-up (V9): 70 days after treatment initiation

The follow up visits will be scheduled as **early** as possible within the window to allow for visits that require rescheduling.

Table 9: Postpartum Follow-up Visits (V5-9)

Postpartum Follow-up Visits 5-9 (V5-9)	
Component	Procedures
Administrative and Regulatory	
 • Review/update locator information • Visit questionnaire • Record/update AEs • Schedule next visit
Behavioral	
 • Provide modified counseling 
 – Protocol adherence – Study medication use/adherence
Clinical	
 • Review/update medical history • Review/update concomitant medications • Provide study medication with sufficient supply until next visit with 3 additional doses • Provide test results if available • Obtain urine pregnancy test (V7 only)

Laboratory*	Varies by visit: 
 • Visit 6 (4 week postpartum follow up) 
 ◦ HCV RNA ◦ CMP, CBC, GGT • Visit 8 (8 week postpartum follow up) 
 ◦ CMP, CBC, GGT • All other visits: None
--------------------	--

*If necessary, V6 labs can be drawn at V7 and V8 labs can be drawn at V9

End of Treatment Visit (12 week treatment follow-up, V10)

The following procedures will occur at the End of Treatment visit. This visit will be scheduled within 7 days of completion of the 12 week course of study medication. The purpose of this visit will be to collect any remaining study medication and to collect and follow up on any adverse events.

Table 10: End of Treatment Visit

End of Treatment Visit (12 week postpartum follow-up, V10)	
Component	Procedures
Administrative and Regulatory	
 • Review/update locator information • Visit Questionnaire • Record/update AEs • Schedule next visit
Behavioral	
 • Collect remaining study medication and medication administration log • Conduct qualitative interview
Clinical	
 • Review/update medical history • Review/update concomitant medications • Consultation with hepatologist (only if HCV virus not cleared at 8w) • Provide test results if available
Laboratory	
 • HCV RNA • CMP, CBC, GGT

SVR Assessment (3 month post-treatment visit, V11)

The following procedures will occur at the 3 month post-treatment visit

Table 11: SVR Assessment (V11)

SVR Assessment (3 month post-treatment visit, V11)	
Component	Procedures
Administrative and Regulatory	
 • Review/update locator information • Visit Questionnaire • Record/update AEs • Schedule next visit • Conduct qualitative interview
Clinical	
 • Review/update medical history • Provide test results if available • Consultation with hepatologist (by phone)
Laboratory	
 • HCV RNA • CMP, CBC, GGT

9 month post-treatment visit (V12)

The following procedures will occur at the 9 month post-treatment visit (V13)

Table 13: 9 month post-treatment visit (V12)

V13: 9 month post-treatment visit	
Component	Procedures
Administrative and Regulatory	
• Review/update locator information• Review infant demographics/sign release(s) for medical records for infant (if necessary)• Schedule next visit
Clinical	
• Review/update medical history• Provide available test results
Laboratory	
• HCV RNA• CMP, CBC, GGT

End of Study Visit (15 month post-treatment visit, V13)

The following procedures will occur at the End of Study visit (V14). If the participant is unable/unwilling to return to MWH, this visit may be conducted via phone and/or email.

Table 14: End of Study visit (V13)

V14: End of Study Visit	
Component	Procedures
Administrative and Regulatory	
• Review results of infant HCV testing/sign release(s) for medical records for infant (if necessary)•
Clinical	
• Review/update medical history• Provide available test results
Laboratory	
• None

Follow-up Procedures for Participants Who Permanently Discontinue Study Medication

Participants will be permanently discontinued for significant laboratory abnormalities or adverse events as outlined in section 9.3 and 9.4 or if they choose to discontinue the study medication. Participants who are permanently discontinued from the study will be instructed to return the study medication and study medication log. All protocol-specified study procedures will continue for safety except the following:

- Provision of study medication
- Provision of medication use adherence counseling

The following procedures will be performed at the visit in which study medication use is permanently discontinued:

- Viral load as needed (i.e. participant withdraws, investigator opinion)

The participant will be asked to continue in the study and complete all remaining scheduled maternal and infant visits per protocol for safety.

Interim Visits

Interim visits may be performed at any time during the study. Study procedures may be repeated at interim visits as deemed clinically indicated. All interim contacts and visits will be documented in participants' study records and on applicable CRFs.

Adherence Counseling and Assessment

